Medical monitoring: Participants will be given a thorough physical examination prior to study entry. For nicotine administration sessions, participants will be attached to a cardiac monitor as well as a blood pressure and heart rate monitoring device. An IV catheter for nicotine delivery will be in place throughout each test session. Participants will be administered nicotine only if the systolic blood pressure is <150 mmHg and heart rate is <90 beats/minute. Participants will be terminated from the study if the blood pressure at any time is >170/110 mm Hg, if the heart rate is >130 beats/min, or if they develop signs and symptoms consistent with nicotine toxicity. We have not encountered any cases of nicotine toxicity in our nicotine infusion studies. These study procedures were developed as part of our Investigational Tobacco Product (ITP) application to the FDA for IV nicotine.

Overview of the study: We propose a placebo-controlled study that will recruit male and female menthol nicotine dependent smokers. Following screening and evaluation as described above, eligible participants will be enrolled in the study which will last about 4 weeks. Eligible, participants will be randomized to menthol or non-menthol smoking condition for 2 weeks (Phase 1) and then will be switched to the alternative condition for another 2 weeks (Phase 2). The smoking condition will be open label. Participants will be provided with free cigarettes in Phases 1 and 2. For the menthol condition, participants will be provided their usual brand of menthol cigarettes and for the non-menthol condition, they will be provided a matched-brand non-menthol cigarette (e.g., Newport Non-Menthol Gold 100s for those who smoke Newport Menthol Gold 100s). In week 2 of each Phase, participants will have a test session. Each session will include 3 infusions in the following order: nicotine (1 mg per 70 kg body weight to a maximum dose of 1 mg) delivered over 2.5 or 5 minutes, saline delivered over 10 minutes, and nicotine (1 mg/ 70kg to a maximum dose of 1 mg) delivered over 2.5 or 5 minutes). For safety reasons, the maximum dose of nicotine for each infusion will be 1 mg. The infusion rates will be 0.096 and 0.048 µg/kg/second over 2.5 and 5 minutes, respectively. Once the participants complete the test session, participants will be crossed over to the alternative treatment. The period between the 2 Phases will not be longer than one week.

Table 1: Study Overview

Procedures	Study Phases	

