12.3 Data safety and monitoring plan: The Principal Investigator will conduct a review of all adverse events and determine the attribution and grade of severity of the adverse event by using the following scales:

Attribution of Risk Categories:

Definite: Adverse event(s) will clearly be related to investigational agent(s) or other intervention

Probable: Adverse event(s) will likely be related to investigational agent(s)

Possible: Adverse event(s) may be related to investigational agent(s)

Unlikely: Adverse event(s) will doubtfully be related to investigational agent(s)

Unrelated: Adverse event(s) will clearly not be related to the investigational agents(s)

Grades of Risk:

0: No adverse event or within normal limits

1: Mild adverse event

2: Moderate adverse event

3: Severe adverse event resulting in hospitalization or prolongation of existing hospitalization, a persistent or significant disability/incapacity, or a congenital anomaly/birth defect

4: Life-threatening or disabling adverse event

5: Fatal adverse event

Serious adverse events (SAEs) include any untoward medical occurrence that at any dose results in death or the immediate risk of death, hospitalization or the prolonging of an existing hospitalization, persistent or significant disability/incapacity or a congenital anomaly/birth defect. Subjects will be terminated from participation if the investigator feels that subjects' health or well-being may be threatened by continuation in the study. Serious unanticipated and anticipated adverse events will be reported within 48 hours to the VA Hospital and Yale IRB, and NIDA. We will directly report to the FDA, whenever their magnitude or frequency exceeds expectations.

The risk associated with participating in this study is moderate, because nicotine administered may be associated with mild side effects. Serious adverse effects associated with nicotine infusion are not expected.

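### The adverse-event severity scale defines grade 3 by SAE outcomes and puts disability in both grades 3 and 4, so some severe non-serious events cannot be graded above moderate and some disabling events fit two grades (minor)

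*Combined protocol and SAP*

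**What the plan says.** Section 12.3 (Data safety and monitoring plan) has the Principal Investigator review all adverse events and "determine the attribution and grade of severity of the adverse event by using the following scales". Under Grades of Risk, grade 1 is a bare label for mild events, and grade 2 is equally bare: "2: Moderate adverse event". Grade 3 carries a qualifier: "3: Severe adverse event resulting in hospitalization or prolongation of existing hospitalization, a persistent or significant disability/incapacity, or a congenital anomaly/birth defect". The next grade is "4: Life-threatening or disabling adverse event", and grade 5 is a fatal event.

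The same section then defines seriousness on its own terms. It begins "Serious adverse events (SAEs) include any untoward medical occurrence that at any dose results in death or the immediate risk of death" and continues with "hospitalization or the prolonging of an existing hospitalization, persistent or significant disability/incapacity or a congenital anomaly/birth defect". The 48-hour report to the IRBs and NIDA depends on this definition and not on the grade.

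Elsewhere, the Adverse Events entry under Measures provides for the SAFTEE before and after each infusion session, but gives no rule for converting SAFTEE responses to these grades. Section 12.3 also says that the DSMB meets formally three times a year, that the Principal Investigator presents the adverse events there, and that the Board reviews safety data. It specifies no table by grade and no action triggered by a grade.

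**The concern.** Severity is how intense an event is; seriousness is what it leads to. A safety listing needs both, because an intense reaction can pass without lasting consequence. In this scale the step from 2 to 3 is decided by consequence. If the definitions are followed, a severe but non-serious event goes in the same category as a moderate one. If an investigator sees this and grades by judgement instead, the grade departs from the protocol and another rater may not reproduce it.

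The setting makes this more than a theoretical gap. Nicotine is infused under cardiac and blood pressure monitoring with a nurse or physician present. Section 12.3 does not expect serious effects of the infusion. The events to be graded should therefore be mostly non-serious, and it is among those that the scale has no category above moderate, apart from whatever an investigator calls disabling. What is at stake is how faithfully a by-grade safety summary describes tolerability, both to the DSMB and in the final report.

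**Working it through.** No arithmetic applies and the plan gives no figure to reproduce. The check sets the grade definitions beside the SAE definition and then runs example events through both.

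**Step 1: overlap of grade and seriousness.**

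| SAE criterion (section 12.3) | Grade that contains it |
|---|---|
| Death | 5 |
| Immediate risk of death | 4 (life-threatening) |
| Hospitalisation or its prolongation | 3 |
| Persistent or significant disability or incapacity | 3, and also 4 (disabling) |
| Congenital anomaly or birth defect | 3 |

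Every SAE criterion appears in grades 3 to 5. The only entry in those grades that is not plainly an SAE criterion is disability that is neither persistent nor significant, which the bare word in grade 4 could cover. Above grade 2, then, the grade says little about intensity that seriousness does not already say.

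**Step 2: example events, definitions read literally.**

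| Event | SAE? | Grade available |
|---|---|---|
| (a) Moderate, settles in the unit, none of the listed outcomes | No | 2 |
| (b) Severe, settles in the unit, none of the listed outcomes, not life-threatening, not disabling | No | At most 2 |
| (c) Severe, settles in the unit, but significantly incapacitating | Yes | 3, and 4 if also judged disabling |
| (d) Settles in the unit, but was briefly life-threatening | Yes | 4 |
| (e) Severe, leads to admission, not disabling or life-threatening | Yes | 3 |
| (f) Severe, with persistent or significant disability | Yes | Both 3 and 4 |

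Rows (a) and (b) cannot be told apart, which is the gap. Row (f) has two valid grades with no stated boundary, which is the overlap. Row (c) can also have two. Rows (c) and (d) show that the gap is limited: an event that resolves on site can still be graded above 2 if it was incapacitating, disabling or life-threatening.

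**Step 3: where the grade is used.** The 48-hour report uses the SAE definition. Termination uses blood pressure and heart rate limits, signs of toxicity ("or if they develop signs and symptoms consistent with nicotine toxicity", under Medical monitoring, with a matching rule in section 12), or the investigator's judgement of the subject's well-being (section 12.3). The statistical section plans no analysis of adverse-event grade. The grade therefore matters only for description, in whatever listing or summary of adverse events is prepared.

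**The case against.** The strongest case against the point is that nothing described in the plan depends on the grade. Reporting deadlines, termination, sample size and efficacy models would all be the same under a better scale. The overlap at disability changes no report either, because persistent or significant disability is an SAE under both grades. The documents also expect few events: section 11 reports no adverse events from nicotine in more than 100 smokers over five years, and section 12.3 speaks of mild side effects. All of this stands, and it sets the priority.

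A reader might infer more than the text supports, in five ways.

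- *That any reaction settling within the session is capped at moderate.* It is not; see rows (c) and (d).
- *That the DSMB's severity counts are wrong.* The plan describes no counts by grade and the documents contain no event data. The text supports only that such a summary, if prepared, could mislead.
- *That FDA reporting is weakened.* The sentence "We will directly report to the FDA, whenever their magnitude or frequency exceeds expectations" comes directly after the one on serious events, so it most naturally refers to those, and it does not mention grade.
- *That severity comparisons between cigarette conditions or delivery rates would be compressed.* None is planned. Both delivery rates also appear to be given within one session, while the SAFTEE is taken only at its start and end.
- *That crossing a termination limit is the protocol's own example of an under-graded severe event.* The protocol never grades such a crossing or calls it severe.

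What the objection does not remove is the wording itself. This is the only severity scale the documents define, it applies to all adverse events, and the gap and the overlap follow from its text without any outside assumption.

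**Conclusion.** The point holds as a minor defect: a classification rule that is wrong as written. Two faults are established. A severe event with none of the listed outcomes, and neither life-threatening nor disabling, has no grade above 2. An event with persistent or significant disability fits both 3 and 4.

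No number can be put on the effect. It is limited to the events of these two kinds, and the documents give no expected rate for either; the count may be zero. The conclusion assumes that the definitions are applied literally. Its practical effect also assumes that grades are summarised for the DSMB or in the report, which the plan allows but does not require. The documents do not support any consequence for subject protection rules, expedited reporting or the efficacy results.

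**What to change.** Three edits to section 12.3:

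1. Define grade 3 by intensity alone and remove the list of SAE outcomes. The sponsor should choose the descriptor. A short descriptor for grades 1 and 2 would be worth adding at the same time, since both are now bare labels.
2. Keep disability in one grade only.
3. Record seriousness as a separate yes/no item, using the SAE criteria already in the section, and show severity and seriousness side by side in any adverse-event summary, including one for the DSMB.

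The cost is a change of protocol wording and one field on the adverse-event form. Events already graded 2 to 4, if there are any, would need to be checked against the new definitions. The small downside is that the reported number of severe events may rise, because events now limited to grade 2 could be graded 3. The separate seriousness item would show that such a rise is not an increase in SAEs.
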